APPENDIX C
PARTICIPANT DIARY

**Tolerability and Immunogenicity of a Single 40- μ g Dose of Recombinant
Botulinum Vaccine A/B (rBV A/B) for the Production of BabyBIG® in
Volunteers with Existing Botulinum Immunity**

Reaction Recording Sheet – Participant Home Diary

Study Site/Location*: _____ / _____

Participant Study ID Number*: _____

Participant Name: _____

Recombinant vaccine given: Date: _____ / _____ / _____ Time: _____ AM / PM

	1 day 24 hrs	2 days 48 hrs	3 days 72 hrs	4 days 96 hrs	5 days 120 hrs	6 days 144 hrs	7 days 168 hrs
Local reactions:							
Soreness?	Y	N	Y	N	Y	N	Y
Itching?	Y	N	Y	N	Y	N	Y
Erythema? (mm) ^a							
Induration? (mm) ^a							
Systemic reactions:							
General malaise?	Y	N	Y	N	Y	N	Y
Fatigue?	Y	N	Y	N	Y	N	Y
Lethargy?	Y	N	Y	N	Y	N	Y
Chills, fever?	Y	N	Y	N	Y	N	Y
Lumps, soreness? (not local)	Y	N	Y	N	Y	N	Y
Stiff back, stiff neck?	Y	N	Y	N	Y	N	Y
Nausea, vomiting, or diarrhea?	Y	N	Y	N	Y	N	Y
Other GI symptoms?	Y	N	Y	N	Y	N	Y
Itching, hives?	Y	N	Y	N	Y	N	Y

^a Please use tool provided to measure. Please list any medications used to treat the potential reactions above:

If you answered **yes** to any of the above potential reactions, please record additional comments i.e., date/time of reaction, symptoms

If additional space required, please continue on back of this form.

* To be filled in by study staff

Ver. August 2018

APPENDIX D
DONOR HISTORY QUESTIONNAIRE

**PPTA Abbreviated Donor History Questionnaire
For Frequent Plasma Donors**

This document is one component of the PPTA donor history questionnaire documents to be used by source plasma organizations. The PPTA abbreviated donor history questionnaire documents must be used collectively.

**PPTA Abbreviated Donor History Questionnaire
For Frequent Plasma Donors**

Current Health	Yes	No
1. Are you feeling healthy and well today?		

Please Read the Medication List

2. Since you last donated plasma have you taken any medications on the medication list?		
---	--------------------------	--------------------------

Changes in Health

Since you last donated plasma:

	Yes	No
3. Female Donors: Have you been pregnant or are you pregnant now?		
4. Have you had any new medical problems or diagnoses?		
5. Have you had any new medical treatments, vaccinations or medications?		
6. Have you had contact with someone who had a smallpox vaccination?		
7. Have you donated whole blood, platelets or plasma at another center?		

Risk Activities

Please review our Risk Poster

8. Did you review the Risk Poster?		
9. Do you have any questions about anything mentioned on the Risk Poster?		
10. Since you last donated plasma, does anything on the Risk Poster apply to you?		

Since you last donated plasma:

11. Have you gotten a tattoo or had one touched up?		
12. Have you had an ear or body piercing?		

**PPTA Abbreviated Donor History Questionnaire
For Frequent Plasma Donors**

Yes No

Optional Question A. Have you had surgery or a diagnostic, medical or dental procedure?

Optional Question B. Have you had acupuncture?

Additional Questions:

Acknowledgment:

1. I have reviewed the educational materials regarding infections that can be transmitted by my donation, such as, Syphilis, HIV, Hepatitis B and C.
2. I agree not to donate if my donation could result in a potential risk to people who receive plasma products.
3. A sample of my blood will be tested for infections that can be transmitted by my donation, such as, Syphilis, HIV, Hepatitis B and C.
4. I understand you will attempt to notify me if for any reason I cannot donate and records will be maintained indicating the reason for the deferral and the deferral time period.
5. I have reviewed the information regarding the potential risks and hazards of donating Source Plasma.
6. I have been given the opportunity to ask questions and understand that I may withdraw from the donation procedure at any time.

Donor Signature: _____ **Date:** _____

APPENDIX E

ADVERSE EVENT RECORDING SHEET FOR IDENTIFICATION OF POSSIBLE SERIOUS ADVERSE EVENTS (SAES)

Tolerability and Immunogenicity of a Single 40- μ g Dose of Recombinant Botulinum Vaccine A/B (rBV A/B) for the Production of BabyBIG® in Volunteers with Existing Botulinum Immunity

Adverse Events Recording Sheet for Identification of Possible Serious Adverse Events (SAEs)

Study Site/Location*: _____ / _____ Participant Study ID Number*: _____

Participant Name: _____

Recombinant vaccine given: _____ Date: _____ / _____ / _____ Time: _____ AM / PM

- You may or may not experience any adverse events. The purpose of this recording sheet is for you to document at home any adverse events during the course of the study, if such should occur.
- If you make an error while recording, please draw a single line through the error, add your correction and initial. Please no white out or multiple lines through errors.
- The information you document on this form will be queried for by study staff during on-site study visits and phone call follow-up for safety at Weeks 1, 4, 10 and 26.
- Please indicate the date and time (if relevant) of each event's occurrence, as well as the date/time of the event's resolution.
- Please categorize the event's severity as indicated below.

Note: If you experience severe, life-threatening or any of the following neuromuscular symptoms (blurred or double vision, drooping of eyelids, drooping of the mouth, dry mouth, difficulty swallowing, difficulty speaking, weakness of an arm or leg, lack of coordination, shallow breathing, sensitivity to sunlight, or inability to perspire), **please seek medical attention immediately and notify [name] (24/7/365 [contact]) or [name] (24/7/365 [contact]) as soon as possible.**

*Please categorize the severity of the reaction as:

mild	= you are able to perform all routine daily activities
moderate	= you are able to perform some routine activities, but are limited in others
severe	= you are unable to perform all routine activities, often seeking medical care

#	Reaction or Event Description/Location	New Event? (Y/N)	Date / Time Started	Date / Time Ended	Severity	Treatment	Comments

Additional Comments, if any (please continue on reverse side).

* To be filled in by study staff

Ver. August 2018

Site Investigator's Initials _____

**Tolerability and Immunogenicity of a Single 40- μ g Dose of Recombinant
Botulinum Vaccine A/B (rBV A/B) for the Production of BabyBIG® in Volunteers
with Existing Botulinum Immunity**

**Adverse Events Recording Sheet for Identification of Possible Serious
Adverse Events (SAEs)**

Study Site/Location*: _____ / _____ Participant Study ID Number*: _____

Additional Comments, if any:

Reviewed by: _____ Date: ____ / ____ / ____ Time: ____ AM/PM
Site Principal Investigator or Designee

Title: _____

* To be filled in by study staff

Ver. August 2018

Site Investigator's Initials _____

1.0 STUDY INTRODUCTION

1.1 BACKGROUND

Botulism Immune Globulin Intravenous (Human) (BIG-IV; BabyBIG®) has been demonstrated to significantly shorten hospital stay and improve outcomes in infant botulism patients. It is currently produced from antibodies collected from persons with existing botulinum immunity including individuals previously immunized with investigational pentavalent botulinum toxoid (PBT) for occupational protection and/or boosted with investigational recombinant botulinum vaccine A/B (rBV A/B).

Previously, PBT was distributed through the Centers for Disease Control and Prevention (CDC) under BB-IND-0161 for occupational safety. The toxoid was administered to naïve recipients and was also administered as a booster in persons who had been previously immunized. PBT-immunized individuals who have circulating antibodies against botulinum toxin type A and type B are eligible to donate plasma for manufacture of BabyBIG. Donated plasma is fractionated and treated to yield a purified immunoglobulin G product that provides passive immunity to patients with infant botulism.

However, the CDC no longer provides investigational PBT for immunization of laboratory workers at risk for occupational exposure to botulinum serotypes A, B, C, D, and E. Specifically, on the basis of evidence of declining immunogenicity, increasing reactogenicity, and the age of the product, the CDC ceased distribution of PBT after 30 November 2011. Thus, a new immunogen against botulinum toxins is needed.

A recombinant botulinum vaccine for the toxin serotypes A and B (rBV A/B) has been developed and is being proposed as a replacement immunogen for boosting individuals who previously received the PBT for occupational protection. This study is the second phase 2 study under IND 15155 being conducted by the California Department of Public Health (CDPH) to determine if rBV A/B will stimulate production of neutralizing antibodies against botulinum toxin types A and B in participants previously immunized with PBT (or PBT and rBV A/B). Participants with a range in neutralizing antibody titers against the toxin types would be candidates for plasma collection for BabyBIG production under IND 15155.

This protocol has as its ultimate goal the production of additional lots of the approved orphan drug BabyBIG for the treatment of the rare disease infant botulism. To enable production of BabyBIG, a group of high-titer immunized persons are needed who are willing to donate their hyperimmune plasma as a starting agent (i.e., Source Plasma) for BabyBIG. This protocol is designed to determine botulinum toxin type A and type B neutralizing antibody levels in healthy participants who were previously immunized with PBT (or PBT and rBV A/B) for occupational protection and who receive rBV A/B (or an rBV A/B boost). A Phase 2b study conducted by CDPH (rBV A/B-CL-001) from 2013 to 2015 demonstrated a single 40- μ g dose of rBV A/B was well tolerated and resulted in a significant increase in neutralizing antibodies against botulinum toxins type A and B in participants previously immunized with PBT. The proposed study (rBV A/B-CL-002) will continue to evaluate the immunogenicity and tolerability of a single dose of the rBV A/B vaccine in this population of individuals with existing botulinum immunity. This study design is similar to rBV A/B-CL-001. However, in this study a single 40- μ g dose of rBV A/B will be used to stimulate the production of neutralizing antibodies against botulinum toxin type A and type B in participants that are either rBV A/B naïve or in participants that volunteered for the rBV A/B-CL-001 clinical study and received one dose of rBV A/B.

1.2 STUDY OBJECTIVES

1.2.1 Immunogenicity

The immunogenicity objective of this study is to evaluate the effects of a single 40- μ g dose of rBV A/B on botulinum toxin type A and type B neutralizing antibody concentrations (NAC) over a 12-week period following vaccination in participants previously immunized with PBT (or PBT and rBV A/B) for occupational protection.

1.2.2 Safety

The safety objective of this study is to obtain safety information during the 12-week study period and at 6 months post-vaccination on the use of rBV A/B in a population of participants previously immunized with PBT (or PBT and rBV A/B) for occupational protection.

1.2.3 Exploratory

The exploratory objective of this study is to collect source plasma from participants that contains neutralizing antibodies against botulinum toxin type A and type B for the production of BabyBIG.

1.3 STUDY DESIGN

This will be an open-label, uncontrolled study to evaluate the safety and immunogenicity of a single intramuscular injection of 40 µg of rBV A/B in participants who were previously immunized with PBT (or PBT and rBV A/B) for occupational protection. Participants will receive the rBV A/B injection and may elect to undergo plasmapheresis at a maximum of two times per week for up to 12 weeks post-vaccination. Participants continue plasmapheresis for up to 14 weeks post-vaccination as long as they continue to meet source plasma donor acceptance criteria.

The study period is defined as the 12-week period that includes the clinic visits and plasmapheresis visits. The study period will end at Week 4 for participants who opt not to participate or who have been determined to be ineligible for donation for the entire study. Participants undergoing plasmapheresis will also have an additional hematology specimen collected at Week 4 and will have a final on-site study visit at Week 12. All participants will have a final phone call for safety follow-up at Week 26.

1.4 SAMPLE SIZE

No formal power calculations were performed for this study. The sample size will consist of up to 50 participants. On the basis of prior Sponsor-Investigator experience, this sample size is considered adequate for fulfilling the study objectives.

1.5 RANDOMIZATION

This is an open-label study, and no randomization or blinding will take place.

1.6 STUDY PROCEDURES

The study will begin with a 7-day screening period (Days -7 to -1), during which participant eligibility will be determined. Screening must occur 1 to 7 days before the Vaccination Visit (Day 0).

Participants will enter either a 4-week treatment period (for non-plasma donors) or a 12-week treatment period (for plasma donors). At the Vaccination Visit (Day 0), the first day of the treatment period for all subjects, participant eligibility will be reviewed and blood collection will be performed to determine baseline NAC. After these assessments, a single rBV A/B injection will be administered to stimulate the production of antibodies against botulinum toxin type A and type B. Safety assessments will be performed before and after the injection, and a diary will be distributed to the participant to record injection site information, systemic reactions, and concomitant medications over the next seven days.

Study personnel will call all participants at Week 1 (\pm 3 days) to review the diary, injection site reactions, and any potential serious adverse events (SAEs) or new onset chronic illnesses (NOCIs) occurring over the past week.

Participants who receive the rBV A/B vaccination may elect to participate as source plasma donors if they meet the donor eligibility criteria of the sponsor-approved licensed source plasma collection site. Participants who elect to donate source plasma may begin following the Week 1 safety phone call and may donate up to twice per week through Week 12, with the possibility of continuing through Week 14 post-vaccination if they continue to meet source plasma donor eligibility criteria. The assessments to be completed at the visits to the plasma collection center are listed in the protocol and include a blood collection for NAC determination.

Safety assessments for non-plasma donors are scheduled on Week 0, Week 1 (\pm 3 days) (by phone), and Week 4 (\pm 3 days) (final on-site visit). Safety assessments for plasma donors are scheduled at Week 0 with follow-up phone calls at Weeks 1 (\pm 3 days), 4 (\pm 3 days) and 10 (\pm 3 days), and a final on-site study visit at Week 12 (\pm 7 days) to assess general health status and query for the interim occurrence of SAEs or NOCIs, if any.

Within 1 week of Week 26, site personnel will contact all participants by phone to assess their general health status. Interim occurrence of any SAEs or NOCIs will be queried for and recorded. Any concomitant medications used to treat SAEs or NOCIs will be recorded.

NAC sample collections are required for all participants at Week 0 and Week 4. For plasma-donating participants, NAC sample collection is required with each donated unit.

2.0 STUDY POPULATIONS

For this study, up to 50 participants are anticipated to be enrolled. Eligibility will be established by the investigator(s) on the basis of the inclusion and exclusion criteria.

2.1 DEFINITIONS OF POPULATIONS FOR ANALYSIS

2.1.1 Immunogenicity Population

The immunogenicity population will include all participants who receive the vaccine dose, have a baseline NAC, and have at least one post-vaccination immunogenicity assessment up to and including 4 weeks after administration of rBV A/B.

This population will be used for all immunogenicity endpoints.

2.1.2 Per Protocol Population

The per protocol (PP) population will include all participants who receive the vaccine, have a baseline NAC, and have the relevant immunogenicity assessments completed within the protocol-specified timelines (including visit windows) for the time point(s) being summarized and who do not have any major protocol violations expected to affect immunogenicity.

For all summaries and analyses using the PP population, values collected outside the visit windows and values associated with a major protocol violation expected to affect immunogenicity will be excluded from the specific time point being summarized or analyzed.

This population will be used in the case that any sensitivity analyses are deemed necessary.

2.1.3 Safety Population

The safety population will include all participants enrolled into the study who receive the vaccine dose and have at least one post-baseline safety assessment [this assessment can include a response from a participant that no adverse events (AEs) occurred].

2.1.3 Plasma-Donating Population

The plasma-donating population will include all participants who receive the vaccine and donate at least one plasma unit. This population will be used for the exploratory endpoint described in Section 9.0.

2.2 PROTOCOL VIOLATIONS

Determination of major protocol violations expected to affect immunogenicity for each participant (and hence affecting the PP population) will be performed by the Sponsor-Investigator before reviewing the immunogenicity data for the applicable participant.

All protocol deviations will be documented and listed in an appendix listing of the clinical study report.

3.0 SPECIFICATIONS FOR STATISTICAL ANALYSES

3.1 GENERAL INFORMATION AND DATA COLLECTION METHODS

All statistical analyses will be performed and data displays will be created using SAS® Release 9.4 or newer.

Summary tables of data will be provided as appropriate, showing the number of participants with non-missing data (n), mean, standard deviation, median, minimum and maximum for continuous variables, and counts and percentages for categorical variables. Appendix listings will also be provided for the clinical study report.

Data will be recorded in electronic case report forms (eCRFs). Clinical laboratory data and NAC data will come from external vendors.

For all summaries and analyses, including those involving change from baseline endpoints or baseline covariates, a participant's baseline value will be defined as the last non-missing value prior to vaccination.

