2.0 OBJECTIVES**2.1 IMMUNOGENICITY**

The immunogenicity objective of this study is to evaluate the effects of a single 40- μ g dose of rBV A/B on the botulinum toxin type A and type B neutralizing antibody concentration (NAC) over a 12-week period following vaccination in participants previously immunized with PBT (or PBT and rBV A/B) for occupational protection.

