8.2 STATISTICAL ANALYSIS

8.2.1 General Overview

The data will be summarized in tables listing the mean, standard deviation or standard error, median, minimum, maximum and number of participants for continuous data or in tables listing count and percentage for categorical data, where appropriate. Data will be listed by “participant ID.” All statistical analyses will be performed and data appendices will be created by using SAS.

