3.2 ENDPOINTS

3.2.1 Immunogenicity Endpoints

The primary immunogenicity endpoint is the proportion of participants achieving a four times or greater increase in NAC by Week 4 compared with Week 0. A positive response will be defined as achieving this level of increase in at least 50% of the participants for botulinum toxin type A and type B.

The secondary immunogenicity endpoints are as follows:

- The proportion of participants achieving a two times increase in the area under the plasma concentration-time curve between Week 0 and Week 12 in NAC in comparison to a straight-line extension of the Week 0 NAC to Week 12. A positive response will be defined as achieving this level of increase in at least 50% of the participants for botulinum toxin type A and type B.

- The proportion of participants achieving a three times or greater increase in NAC by Week 4 compared with Week 0. A positive response will be defined as achieving this level of increase in at least 50% of the participants for botulinum toxin type A and type B.

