7.1 ANALYSIS OF PRIMARY IMMUNOGENICITY ENDPOINT

The primary immunogenicity endpoint is the proportion of participants achieving a four times or greater increase in NAC by Week 4 compared to Week 0. The cut-off value for determining whether the increase is achieved for each subject will be calculated as $[(\text{Week 0 value}) \times 4] + (\text{Week 0 value})$. A positive response will be defined as achieving this level of increase in NAC in at least 50% of participants. The proportion of participants who achieve this level of increase in NAC will be provided along with a 95% confidence interval. Graphs may be used to show corresponding participant-level data.

This primary analysis will be performed for both botulinum toxin type A and type B. In the event that the primary endpoint is not met for neutralizing antibodies against botulinum toxin type A or type B, the Sponsor-Investigator will determine if the plasma collected during the study contains sufficient antibody titers for meeting specifications for BabyBIG production. If so, the trial will still be considered successful.

Details regarding the collection schedule for blood samples for NAC can be found in Section 7.3.

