7.3 NEUTRALIZING ANTIBODY CONCENTRATION (NAC) VALUES

NAC determinations will be performed at Battelle Biomedical Research Center (Columbus, Ohio) by using a fully validated mouse neutralization assay used for all NAC determinations in the BabyBIG program.

Blood collection for determination of NAC values will be performed prior to vaccination at the Vaccination Visit (Day 0), for non-plasma donating participants at the Week 4 visit, and for plasma-donating participants at plasmapheresis visits and the Week 12 final study.

For summary tables involving NAC values, the week numbers will be assigned as described below. Week 4 and Week 12 have larger windows than other weeks in order to facilitate collection of NAC values during the time periods of primary interest.

Week 1 - values collected from Day 4 through Day 10

Week 2 - values collected from Day 11 through Day 17
Week 3 - values collected from Day 18 through Day 23
Week 4 - values collected from Day 24 through Day 32 [Day 28 (± 4 days)]
Week 5 - values collected from Day 33 through Day 38
Week 6 - values collected from Day 39 through Day 45
Week 7 - values collected from Day 46 through Day 52
Week 8 - values collected from Day 53 through Day 59
Week 9 - values collected from Day 60 through Day 66
Week 10 - values collected from Day 67 through Day 73
Week 11 - values collected from Day 74 through Day 79
Week 12 - values collected from Day 80 through Day 88 [Day 84 (± 4 days)]
Week 13 - values collected from Day 89 through Day 94
Week 14 - values collected from Day 95 through Day 101

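### Weekly NAC is summarised only on the arithmetic scale, and no estimate with a confidence interval of the size of the within-person rise is planned

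*SAP*

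**What the plan says.** Protocol 8.2.1 sets one rule for all continuous data: "mean, standard deviation or standard error, median, minimum, maximum and number of participants for continuous data". SAP 3.1 repeats it as n plus "mean, standard deviation, median, minimum and maximum for continuous variables". SAP 7.3 then says "For summary tables involving NAC values, the week numbers will be assigned as described below" and lists day windows for Weeks 1 to 14. It names no statistic for those tables, so the general rule applies. Neither document mentions a geometric mean, a log transformation, or any summary of each participant's ratio to baseline.

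The immunogenicity endpoints are all responder proportions based on a ratio to baseline:

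- Primary (SAP 7.1): "The primary immunogenicity endpoint is the proportion of participants achieving a four times or greater increase in NAC by Week 4 compared to Week 0".
- First secondary (SAP 3.2.1): "The proportion of participants achieving a two times increase in the area under the plasma concentration-time curve between Week 0 and Week 12 in NAC", compared with the Week 0 level carried forward.
- Second secondary (SAP 3.2.1): "The proportion of participants achieving a three times or greater increase in NAC by Week 4 compared with Week 0".

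Each proportion gets a 95% confidence interval (SAP 7.1 and 7.2). Participant-level graphs are optional (SAP 7.1).

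The objective in Protocol 2.1 is wider than a responder count. It concerns the vaccine's effect on "neutralizing antibody concentration (NAC) over a 12-week period following vaccination".

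**The concern.** The endpoint definitions treat NAC as a quantity that changes by multiplication, while the summary rule treats it as one that changes by addition. When titers are spread over a wide multiplicative range, the arithmetic mean lies above the typical participant and the SD is hard to interpret.

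The larger loss is what goes unreported. The study is uncontrolled and has up to 50 participants, so the within-person change is its main measure of vaccine effect. The plan reduces that change to yes or no at fixed thresholds. A reader of the report would learn what share of participants passed the threshold for toxin A and for toxin B. The reader would not learn how large the average rise was or how precisely it was estimated, although the data to say so are collected.

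**Working it through.** The plan states no NAC variance, expected fold-rise or power figure, so there is nothing of its own to reproduce. All spreads below are assumptions.

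**1. Arithmetic against geometric mean.** Take NAC as log-normal and let s = ln(10) × (log10 SD). Then arithmetic mean / geometric mean = exp(s²/2), and the share of participants below the arithmetic mean = Φ(s/2).

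| log10 SD (assumed) | s | mean / geometric mean | share below the mean |
|---|---|---|---|
| 0.2 | 0.461 | 1.11 | 59% |
| 0.3 | 0.691 | 1.27 | 64% |
| 0.4 | 0.921 | 1.53 | 68% |
| 0.5 | 1.151 | 1.94 | 72% |
| 0.6 | 1.382 | 2.60 | 76% |

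In simulated samples of 50, the five highest values carry 20% of the total at log10 SD 0.2, 27% at 0.3 and 42% at 0.5. The sample median stays at about 1.0 times the geometric mean throughout.

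**2. Reading a fold-rise off the weekly tables.** The true geometric mean fold-rise was set at 5, because the SAP 7.1 cut-off (four times the Week 0 value plus the Week 0 value) equals 5 times baseline. Assumptions: n = 50, 10,000 replicates, baseline log10 SD 0.3 to 0.7, slope of log fold-rise on log baseline 0 to −0.8, residual log10 SD 0.3 to 0.5. Across scenarios:

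- ratio of arithmetic means: 2.0 to 9.2
- arithmetic mean of individual fold-rises: 6.3 to 19.3
- ratio of medians: 4.97 to 5.03
- geometric mean fold-rise: 4.98 to 5.02

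The ratio of the planned medians is therefore about right on average in these scenarios. The ratio of the planned means may not be.

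**3. Precision of the medians route.** Assume baseline log10 SD 0.5, log10 SD of individual fold-rise 0.4, no link between the two, n = 50 and true rise 5. The paired geometric mean fold-rise has a 95% range of 5 × 10^(±1.96 × 0.4/√50) = 5 × 10^(±0.111), or about 3.9 to 6.5. The ratio of medians, simulated with 40,000 replicates, has a 95% range of 3.3 to 7.6. With fold-rise SD from 0.3 to 0.5, its log-scale variance is about 3.3 down to 2.4 times that of the paired estimate. It ignores pairing, so the between-person spread in baseline stays in it.

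**4. Who is in each week.** Under SAP 1.6 and 7.3, everyone is sampled at Weeks 0 and 4. Non-donors have no other scheduled sample, while donors are sampled with each donated unit and at Week 12. The Week 0 summary therefore covers everyone and most later summaries cover donors only.

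Illustration, with half donating, equal log-normal spread and a true 3-fold rise in everyone:

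- If the donors' median baseline is 2 and the non-donors' is 1, the all-participant Week 0 median is √(1 × 2) = 1.41. Donors later have median 2 × 3 = 6, and the tables suggest 6/1.41 = 4.2-fold.
- If the donors' baseline is half that of non-donors, the same arithmetic gives 1.5/0.71 = 2.1-fold.

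A fold-rise computed within participants gives 3 in both cases.

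**The case against.** The strongest reply is that the median, minimum and maximum are already planned, and the median is not pulled by a few high titers. That stands, and it limits the point. A reader might infer that the weekly summaries as a whole will be driven by a few people, but only the mean and SD are exposed, and only if the spread is wide. The documents describe a range of titers without giving a figure.

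Four further replies also stand:

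- A reader might infer that every endpoint is a fold-change. The safety endpoints and plasma volume are not, and the three immunogenicity endpoints are proportions with fold or ratio thresholds.
- A reader might infer that intervals for mean NAC will be unreliable. No such interval is planned, so poor coverage of a normal interval shows no fault in this plan.
- The arithmetic mean need not be removed. The ultimate goal is plasma for BabyBIG, and pooled antibody yield may relate more closely to the arithmetic mean (an inference; the documents give no pooling formula).
- A log-scale summary has a cost. It needs a rule for values below the assay limit and one for repeat values within a week, since donors may give twice weekly. The same-date averaging rule in SAP 7.2 serves only the area-under-the-curve endpoint.

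The reply does not close the gap. The median has no planned interval, it ignores pairing, and in most weeks it describes a different group from Week 0.

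**Conclusion.** The point holds as a gap in the descriptive analysis. As planned, the trial will not report the size of the within-person rise with a confidence interval for either toxin, and its NAC tables stay on the arithmetic scale. That there is no such estimate follows from the documents alone. How far the arithmetic mean departs from the typical titer depends on an assumed log-normal shape and spread: about 1.3 to 2.6 times the geometric mean at log10 SD 0.3 to 0.6, and a minor 1.11 times at 0.2. The donor mismatch is a feature of the sampling schedule, but its size and direction are unknown.

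A reader might infer that the primary conclusion is at risk. The documents do not support that: the responder proportions, their confidence intervals and the 50% rule use each participant's own ratio and never the mean or SD of NAC.

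**What to change.** In SAP 7.3, for each toxin:

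- Add the geometric mean NAC by week with a 95% confidence interval.
- Add the paired geometric mean fold-rise from Week 0 with a 95% confidence interval, computed from within-participant differences in log NAC and back-transformed. Give it at Week 4 for all participants, and at other weeks for those with both values, showing n and noting that these are donors.
- State how values below the assay limit are handled before taking logs.
- Use one value per participant per week, for example the mean of the log values in the window.
- Keep the median, minimum and maximum. The arithmetic mean and SD may stay as secondary statistics.

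This needs no new samples or visits and changes no endpoint. The cost is SAP wording, two extra data rules and a few more table rows. The later-week fold-rises would still describe donors only; pairing removes the baseline mismatch but does not make donors represent everyone.
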